13.6 Safety Analyses

The primary safety endpoint is the proportion of subjects who experience adverse events (through Day 28) leading to study discontinuation. This proportion will be displayed overall for all subjects, and by treatment group

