7.3. Safety Endpoint

Proportion of subjects with adverse events leading to study drug discontinuation [Through Day 28]

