9.2. Subject Withdrawal from Study

Subjects have the right to withdraw consent at any time and for any reason without prejudice to his/her future medical care by the physician or the institution. The specific reason for subject withdrawal of consent will be documented.

If the subject does not wish to continue study assessments, every effort should be made to obtain consent for contact of the subject, or the subject's family member or friends, to establish vital status.

In order to minimize the loss of data, it is critical all subjects are followed for 30 days post cessation of INOpulse therapy unless consent is withdrawn or a subject is lost to follow up.

If at any time, patient care decisions are made based upon resource limitations (eg, availability of PPE), the decision, date and reason should be documented.

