13.1 Subject Disposition

The number (and %) of subjects completing the study, and discontinuing from the study, will be tabulated by treatment group, along with reasons for discontinuation. The number of subjects screened (defined as providing informed consent) and who were screen failures, along with a summary of reasons for screen failure (i.e. eligibility criteria violations), will be provided. A by-subject listing of subjects who signed informed consent but were not randomized (screen failures) including their specific reason for exclusion will also be provided. Subjects who discontinued from the study will be summarized in a by-subject listing.

The number and percentage of subjects in each treatment group in the all randomized, full analysis, and per-protocol analysis sets will be provided.

A tabulation of the number and percentage of enrolled subjects at each center will be presented.

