13.6.2 Adverse Events

Treatment-Emergent Adverse Events (TEAEs) are defined as any AEs with an onset date on or after the date of the first dose of IP or any worsening of a preexisting medical condition/AE with onset after the start of IP and throughout the study. An AE leading to treatment discontinuation is defined as an AE where action taken on study drug is Drug Withdrawn. AEs will be coded using the Medical Dictionary for Regulatory Activities MedDRA version 23.0.

An overall summary of TEAEs, including the number of events reported, the number and percentage of participants reporting at least one TEAE, the number and percentage of participants discontinuing due to an adverse event, the number and percentage of participants with at least one serious adverse event, and the number and percentage of deaths will be presented.

The most frequent adverse events ($\geq 5\%$) will be compared between the INOpulse and placebo groups using a forest plot. The forest plot will display odds ratios of the incidence rate for each AE along with 95% confidence intervals.

A table of all anticipated and unanticipated deaths due to any cause, with number and frequency of such events in each arm/group of the clinical study, as well as the number of occurrences for each event. This also requires notification if the death is causally related to treatment for each reporting group.

A breakdown of the number and percentage of participants reporting each adverse event, categorized by System Organ Class (SOC) and preferred term (PT), will be presented. Note that counting will be by participant not event and participants are only counted once within each SOC and PT.

A further tabulation of these data, categorized by relationship to INOpulse, will be presented. Participants with multiple events within a particular body system or preferred term will be counted under the category of their drug-related event (related and not related) within SOC and PT. Relationship to INOpulse is categorized as related (rated "possible" or "related" in the CRF) or not related (rated "unlikely" or "not related" in the CRF).

A summary of events reported, categorized by severity, will also be provided. Participants with multiple events within a particular SOC and PT will be counted under the category of their most severe event in the following order: severe > moderate > mild within that SOC and PT.

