A summary of adverse events leading to discontinuation of INOpulse will be provided, grouped by body system and preferred term.

The following events will be considered AEs of special interest (AESI). In addition, AESIs will also include medical device deficiencies and/or complaints.

- All respiratory AEs
- Incidence of methemoglobin (MetHb) levels $\geq 7.0\%$ in blood

- New symptoms that may be associated with local nasal irritation: nasal erythema, epistaxis and/or coryza
- New or worsening symptoms of left heart failure or pulmonary edema
- Any decrease in systemic oxygenation measured by either PaO₂ or oxygen saturation by pulse oximeter (SpO₂) deemed by the Investigator to be clinically significant
- New symptoms that may be due to rebound effects associated with a temporal acute withdrawal of study drug (i.e., symptoms occurring within 20 minutes of acute withdrawal and including those associated with device malfunction or failure): hypoxemia, bradycardia, tachycardia, systemic hypotension, syncope, near-syncope, ventricular fibrillation and/or cardiac arrest.

All adverse events (including non-treatment-emergent events) recorded on the CRF will be listed.

Handling of missing or partial AE start dates is defined in Appendix 2.

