Table 14.2.2.5.5	Summary and Analysis of Hospital Duration by No. of Co-Morbidities	All Randomized Analysis Set
Table 14.2.2.6	All-Cause Mortality	All Randomized Analysis Set
Table 14.2.2.6.1	All-Cause Mortality by Race	All Randomized Analysis Set
Table 14.2.2.6.2	All-Cause Mortality by Gender	All Randomized Analysis Set
Table 14.2.2.6.3	All-Cause Mortality by Age Group	All Randomized Analysis Set
Table 14.2.2.6.4	All-Cause Mortality by Baseline Oxygen Level	All Randomized Analysis Set
Table 14.2.2.6.5	All-Cause Mortality by No. of Co-Morbidities	All Randomized Analysis Set

Table Number	Title	Population
Table 14.2.2.7	Disease-Specific Mortality	All Randomized Analysis Set
Table 14.2.2.7.1	Disease-Specific Mortality by Race	All Randomized Analysis Set
Table 14.2.2.7.2	Disease-Specific Mortality by Gender	All Randomized Analysis Set
Table 14.2.2.7.3	Disease-Specific Mortality by Age Group	All Randomized Analysis Set
Table 14.2.2.7.4	Disease-Specific Mortality by Baseline Oxygen Level	All Randomized Analysis Set
Table 14.2.2.7.5	Disease-Specific Mortality by No. of Co-Morbidities	All Randomized Analysis Set
Table 14.2.2.8	Summary of RT-PCR Results by Time Point	All Randomized Analysis Set
Table 14.2.2.8.1	Summary of RT-PCR Results by Time Point by Race	All Randomized Analysis Set
Table 14.2.2.8.2	Summary of RT-PCR Results by Time Point by Gender	All Randomized Analysis Set
Table 14.2.2.8.3	Summary of RT-PCR Results by Time Point by Age Group	All Randomized Analysis Set
Table 14.2.2.8.4	Summary of RT-PCR Results by Time Point by Baseline Oxygen Level	All Randomized Analysis Set
Table 14.2.2.8.5	Summary of RT-PCR Results by Time Point by No. of Co-Morbidities	All Randomized Analysis Set
Table 14.2.2.9	Difference in Proportion in RT-PCR Results at Discharge by Treatment Group	All Randomized Analysis Set
Table 14.3.1.1	Summary of Exposure	Full Efficacy Set
Table 14.3.2.1	Overall Summary of Treatment-Emergent Adverse Events	Full Safety Set
Table 14.3.2.2	Treatment-Emergent Adverse Events by System Organ Class and Preferred Term	Full Safety Set
Table 14.3.2.3	Serious Treatment-Emergent Adverse Events by System Organ Class and Preferred Term	Full Safety Set
Table 14.3.2.4	Treatment-Emergent Adverse Events Leading to Discontinuation of IP by System Organ Class and Preferred Term	Full Safety Set
Table 14.3.2.5	Treatment-Emergent Adverse Events with Outcome of Death by System Organ Class and Preferred Term	Full Safety Set

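### SAP 13.6 words the primary safety endpoint as adverse events leading to study discontinuation, whereas the protocol and SAP 9.0 define it by discontinuation of study drug

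*SAP*

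**What the plan says.** Protocol 7.3 defines the trial's only named safety endpoint: "Proportion of subjects with adverse events leading to study drug discontinuation [Through Day 28". The protocol synopsis has the same definition. SAP 9.0 repeats it as the endpoint attached to the secondary objective, which is safety.

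SAP 13.6, which opens the safety analysis section, names a primary safety endpoint and gives it as the "proportion of subjects who experience adverse events (through Day 28) leading to study discontinuation". The word for drug is absent. The section adds only that the proportion is shown overall and by treatment group. It names no test, analysis set or output table, and it does not refer to the definition that follows in 13.6.2.

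**The concern.** SAP 13.6 is the only place in either document that uses the label primary safety endpoint and says how it will be presented, and the event it names is not the protocol's. Stopping the product and leaving the trial are separate decisions here. A subject who stops INOpulse because of an adverse event and then stays under observation, as the protocol asks, counts under protocol 7.3 and does not count under the literal text of 13.6.

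The literal text could also be programmed without raising a query, because study discontinuation is captured and reported in its own right. At stake is which proportion appears in the report as the trial's safety endpoint. If the mismatch were noticed only after unblinding, choosing between the two definitions would look post hoc.

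**Working it through.** No figure in the plan needs reproducing and no arithmetic applies. The check has three parts.

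**1. Which event does each place name?**

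| Place | Event |
|---|---|
| Protocol synopsis, safety endpoint | Stopping study drug |
| Protocol 7.3 | Stopping study drug |
| SAP 9.0 | Stopping study drug |
| SAP 13.6 | Leaving the study |
| SAP 13.6.2, definition | Stopping study drug: "An AE leading to treatment discontinuation is defined as an AE where action taken on study drug is Drug Withdrawn" |
| SAP 13.6.2, planned summary | Stopping study drug: "A summary of adverse events leading to discontinuation of INOpulse will be provided" |
| SAP Appendix 4, Table 14.3.2.4 | Stopping study drug: "Treatment-Emergent Adverse Events Leading to Discontinuation of IP by System Organ Class and Preferred Term", on the Full Safety Set |
| SAP 13.6.2, overall TEAE summary | Unclear: counts participants who discontinue because of an adverse event, without saying from what |

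SAP 13.6 is the only entry that names leaving the study. The term used in the 13.6.2 definition, treatment discontinuation, is tied to the action recorded for study drug. It is the same concept as the protocol endpoint and not an additional one.

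**2. Are the two events really different in this trial?**

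- Protocol 9.1 deals with stopping the drug or device, and protocol 9.2 deals with withdrawal from the study.
- Protocol 9.2 says that "it is critical all subjects are followed for 30 days post cessation of INOpulse therapy unless consent is withdrawn", with loss to follow-up as the other exception. The Early Discontinuation footnote to the schedule of assessments repeats the 30-day requirement.
- SAP 13.1 handles leaving the study as disposition: the number of subjects "discontinuing from the study, will be tabulated by treatment group, along with reasons for discontinuation".
- Appendix 4 has separate listings for discontinued subjects (16.2.1.1) and for discontinuation of investigational product (16.2.1.2).

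So the events are distinct. They can overlap: a subject who leaves the study during treatment because of an adverse event has also stopped drug. The subjects at issue are those who stop drug for an adverse event and remain in follow-up.

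**3. Does the planned table supply the endpoint as it stands?**

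Not quite. Table 14.3.2.4 is organised by system organ class and preferred term. Its title shows no Day 28 limit, and it is not labelled as the safety endpoint. SAP 13.6.2 defines treatment-emergent events as running throughout the study, and protocol follow-up extends to 30 days after the last dose. Dosing itself ends at Day 28 at the latest, so the limit may exclude few events, but it is part of the endpoint and should be stated.

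**The case against.** The strongest reply is that the SAP already carries out the protocol's endpoint. SAP 9.0 states it correctly, 13.6.2 defines it through Drug Withdrawn and plans a summary, and Table 14.3.2.4 reports it on the Full Safety Set. Appendix 4 lists no table of adverse events leading to study discontinuation. On this view 13.6 has lost a word, and any statistician reading the whole SAP would supply it. Nothing is tested on this endpoint, and safety is also covered by the summaries of serious events, deaths and events of special interest and by at least monthly unblinded DMC review.

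Most of that stands. It shows what was intended and limits the consequence. A reader might infer from 13.6 that the trial could not detect a tolerability problem. The documents do not support that, because adverse events leading to withdrawal of INOpulse will be tabulated in any case.

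It does not remove the error. The sentence that presents the endpoint still names the wrong event, does not point to the definition that would correct it, and leaves no table identified as the endpoint.

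**Conclusion.** The point holds as an inconsistency within the SAP, and between SAP 13.6 and the protocol, most likely from a dropped word. It affects what is reported as the only named safety endpoint. It has no effect on sample size, power or type I error.

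Its numerical size cannot be given, because the documents state no expected rate for discontinuing drug or for discontinuing the study because of an adverse event. Two stronger readings are tempting and should not be adopted:

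- A reader might infer that the literal endpoint would be far rarer, or close to zero. Continued follow-up makes a lower count plausible, but the SAP does not say whether a fatal adverse event counts as study discontinuation, and no figure supports the size of the gap.
- A reader might use the 15% and 6% planning rates in SAP 8.1 to count subjects who stop drug for respiratory failure. Those rates are applied to the death-or-respiratory-failure composite through Day 28, which includes deaths and events after dosing has ended. Dosing also stops at resolution of hypoxemia or at discharge. Respiratory failure is an SAE under protocol 13.1.5 and ends dosing, but the documents do not say that such cases are recorded as Drug Withdrawn.

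The conclusion rests only on the wording of the sections compared and on the protocol's rule that subjects stay in follow-up after stopping drug.

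**What to change.** In SAP 13.6, replace *study discontinuation* with *study drug discontinuation (AE with action taken on study drug = Drug Withdrawn, as defined in 13.6.2), with onset through Day 28*. State that the proportion is calculated on the Full Safety Set and shown overall and by treatment group.

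Report it as an any-event row restricted to Day 28 in Table 14.3.2.4, or in an added table, and name that table in 13.6. In the overall TEAE summary in 13.6.2, say that the discontinuation counted is from study drug.

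The cost is one corrected sentence, one clarifying phrase and one table row. SAP 1.0 is marked final, so under SAP 6.0 the change belongs in an amendment. It should be made before unblinding. No data collection or sample size changes.

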13.6.1 Data Monitoring Committee Review

This study will utilize an independent DMC to monitor and review data periodically throughout the trial, at a minimum monthly, as described in the current DMC charter on file with the sponsor. Adverse events will be summarized in tables for all patients and by treatment group. Patient listings will also be provided. The analysis will include all patients in the ARAS, and the data will be unblinded to the DMC. Treatment futility will be determined after 100 patients have been on-study for up to 28 days. The stopping rule criteria for futility using the interim analysis data are described in Section 12.1 of this SAP.

13.6.2 Adverse Events

Treatment-Emergent Adverse Events (TEAEs) are defined as any AEs with an onset date on or after the date of the first dose of IP or any worsening of a preexisting medical condition/AE with onset after the start of IP and throughout the study. An AE leading to treatment discontinuation is defined as an AE where action taken on study drug is Drug Withdrawn. AEs will be coded using the Medical Dictionary for Regulatory Activities MedDRA version 23.0.

An overall summary of TEAEs, including the number of events reported, the number and percentage of participants reporting at least one TEAE, the number and percentage of participants discontinuing due to an adverse event, the number and percentage of participants with at least one serious adverse event, and the number and percentage of deaths will be presented.

The most frequent adverse events ($\geq 5\%$) will be compared between the INOpulse and placebo groups using a forest plot. The forest plot will display odds ratios of the incidence rate for each AE along with 95% confidence intervals.

A table of all anticipated and unanticipated deaths due to any cause, with number and frequency of such events in each arm/group of the clinical study, as well as the number of occurrences for each event. This also requires notification if the death is causally related to treatment for each reporting group.

A breakdown of the number and percentage of participants reporting each adverse event, categorized by System Organ Class (SOC) and preferred term (PT), will be presented. Note that counting will be by participant not event and participants are only counted once within each SOC and PT.

A further tabulation of these data, categorized by relationship to INOpulse, will be presented. Participants with multiple events within a particular body system or preferred term will be counted under the category of their drug-related event (related and not related) within SOC and PT. Relationship to INOpulse is categorized as related (rated "possible" or "related" in the CRF) or not related (rated "unlikely" or "not related" in the CRF).

A summary of events reported, categorized by severity, will also be provided. Participants with multiple events within a particular SOC and PT will be counted under the category of their most severe event in the following order: severe > moderate > mild within that SOC and PT.

A summary of adverse events leading to discontinuation of INOpulse will be provided, grouped by body system and preferred term.

The following events will be considered AEs of special interest (AESI). In addition, AESIs will also include medical device deficiencies and/or complaints.

- All respiratory AEs
- Incidence of methemoglobin (MetHb) levels $\geq 7.0\%$ in blood

- New symptoms that may be associated with local nasal irritation: nasal erythema, epistaxis and/or coryza
- New or worsening symptoms of left heart failure or pulmonary edema
- Any decrease in systemic oxygenation measured by either PaO₂ or oxygen saturation by pulse oximeter (SpO₂) deemed by the Investigator to be clinically significant
- New symptoms that may be due to rebound effects associated with a temporal acute withdrawal of study drug (i.e., symptoms occurring within 20 minutes of acute withdrawal and including those associated with device malfunction or failure): hypoxemia, bradycardia, tachycardia, systemic hypotension, syncope, near-syncope, ventricular fibrillation and/or cardiac arrest.

All adverse events (including non-treatment-emergent events) recorded on the CRF will be listed.

Handling of missing or partial AE start dates is defined in Appendix 2.

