7.0 Study Objectives

The study protocol objectives are as follows:

Primary Objective: To verify the efficacy of INOpulse in subjects with COVID-19.

Secondary Objective: To evaluate the safety of INOpulse in subjects with COVID-19.

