13.6.3 Deaths and Serious Adverse Events

The number and percentage of subjects reporting a SAE, by SOC and PT will be summarized by treatment group.

All deaths and SAEs will be presented in a by-subject level listing.

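### SAP 13.6 plans no between-arm estimate or confidence interval for the trial's one safety endpoint; its only AE contrast is an odds ratio plot limited to events at 5% or more

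*SAP*

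**What the plan says.** SAP 7.0 gives safety as the second of two objectives: "Secondary Objective: To evaluate the safety of INOpulse in subjects with COVID-19". Protocol 7.3 attaches a single endpoint to it: "Proportion of subjects with adverse events leading to study drug discontinuation [Through Day 28"]. SAP 9.0 repeats that endpoint.

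The whole planned analysis of this endpoint in SAP 13.6 is: "This proportion will be displayed overall for all subjects, and by treatment group".

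SAP 13.6.2 contains one comparison of the arms on AEs: "The most frequent adverse events ($\geq 5\%$) will be compared between the INOpulse and placebo groups using a forest plot". The measure is fixed in the next sentence: "The forest plot will display odds ratios of the incidence rate for each AE along with 95% confidence intervals". No interval method, no rule for zero cells and no denominator for the 5% are given.

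The remaining AE outputs are descriptive. For each AE term there is "A breakdown of the number and percentage of participants reporting each adverse event". For SAEs, SAP 13.6.3 has: "The number and percentage of subjects reporting a SAE, by SOC and PT will be summarized by treatment group". SAP 13.6.2 names AEs of special interest, for example "Incidence of methemoglobin (MetHb) levels $\geq 7.0\%$ in blood". Appendix 4 has no table for them, and methemoglobin appears only as Listing 16.2.12.

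**The concern.** A trial with safety as a stated objective should be able to report how much more often the safety endpoint occurred on active drug than on placebo, and how precisely that is known. The SAP does this for efficacy. Section 13.5.4 gives the primary endpoint an odds ratio and a difference in proportions, each with a 95% CI. Sections 13.5.5.2, 13.5.5.3 and 13.5.5.5 give recovery, discharge and mortality per-arm intervals and a chi-square test. The safety endpoint gets none of these.

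The one safety contrast that is planned uses a measure that degenerates when an event occurs only on active drug, which is a pattern a safety display should show clearly. It also stops at a frequency cut whose denominator is undefined, so AEs of special interest below that cut have no planned contrast.

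**Working it through.** **Inputs.** SAP 8.1 gives 500 subjects randomized 1:1. SAP 11.2 defines the Full Safety Set as randomized and dosed subjects. I assume 250 per arm. All AE counts below are illustrative, because the documents give no expected AE rates and no precision target for safety. There is thus no safety figure of the plan's own to reproduce.

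**1. Which safety outputs contrast the arms?** I read SAP 13.6 to 13.6.6 against Appendix 4. Tables 14.3.2.1 to 14.3.2.9 are counts, percentages or subject-level displays. Laboratory and vital-sign tables are descriptive. Only Figure 14.2.1.1, the forest plot, carries a between-arm estimate. The safety endpoint is an aggregate over AE terms, so it is not one of the plotted AEs.

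**2. The 5% cut in counts.** In one arm: 0.05 × 250 = 12.5, so 13 subjects. Pooled: 0.05 × 500 = 25 subjects.

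**3. Zero events on placebo, 13 vs 0.**
- Sample odds ratio: (13 × 250)/(0 × 237), not finite.
- Wald standard error of the log odds ratio: √(1/13 + 1/0 + 1/237 + 1/250), undefined.
- Conditional exact 95% CI: 3.16 to infinity.
- Adding 0.5 to each cell: (13.5 × 250.5)/(0.5 × 237.5) = 28.5, Wald 95% CI 1.7 to 482.
- Risk difference: 13/250 − 0/250 = 5.2 points, score 95% CI 3.1 to 8.7.

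The score (Miettinen-Nurminen) interval is the set of differences d for which |(p_T − p_C − d)/√V(d)| ≤ 1.96. Here V(d) = [q_T(1 − q_T)/250 + q_C(1 − q_C)/250] × 500/499, and q_T, q_C are the maximum likelihood rates subject to q_T − q_C = d.

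The odds ratio display thus depends on a method that the SAP does not name. On the either-arm reading this problem starts at 13 vs 0. On the pooled reading 13 vs 0 is 13/500 = 2.6% and is not plotted, so the problem starts at 25 vs 0.

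**4. What the two readings of 5% leave out.**

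| INOpulse vs placebo | Rates | Fisher p | Pooled | Plotted, pooled reading | Plotted, either-arm reading |
|---|---|---|---|---|---|
| 13 vs 0 | 5.2% vs 0% | 0.0002 | 2.6% | no | yes, no finite OR |
| 24 vs 0 | 9.6% vs 0% | <0.000001 | 4.8% | no | yes, no finite OR |
| 20 vs 4 | 8.0% vs 1.6% | 0.001 | 4.8% | no | yes, finite OR |
| 12 vs 2 | 4.8% vs 0.8% | 0.01 | 2.8% | no | no |

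The chance that a true harm reaches the plot on the either-arm reading is 1 − P(X_T ≤ 12) × P(X_C ≤ 12), with binomial counts on 250. For true rates of 3% vs 0.5% it is about 4% (pooled reading: about 0%). For 5% vs 1% it is 48% (pooled: 1%).

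**5. The safety endpoint itself.** Two assumed outcomes, with score 95% CIs:
- 15 vs 5 (6.0% vs 2.0%): difference 4.0 points, 0.6 to 7.9.
- 10 vs 4 (4.0% vs 1.6%): difference 2.4 points, −0.6 to 5.8.

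The planned display would print the percentages. It would not print the intervals, one of which excludes zero and one of which does not.

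**The case against.** The strongest reply is that no information is lost. SAP 13.0 makes summaries by treatment group the default. Every AE term gets counts and percentages whatever its frequency (Table 14.3.2.2), SAEs likewise (Table 14.3.2.3), and AEs leading to discontinuation have Table 14.3.2.4. Anyone can subtract two percentages. This stands. A reader might infer that rarer harms and the safety endpoint are left with no estimate at all, or that 6% vs 2% could not be told apart from 4% vs 1.6%. The documents do not support either, because the per-arm figures are shown. What is not planned is the contrast with its interval.

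A reader might also infer that an odds ratio interval cannot be obtained with a zero cell. That is too strong: the exact lower limit of 3.16 for 13 vs 0 is usable. The defect is that the SAP names no method and the point estimate is not finite.

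Nor is the forest plot the trial's only comparison of harm. SAP 13.5.5.5 tests all-cause and cardiopulmonary mortality, the latter built from fatal respiratory AEs. Respiratory failure, an SAE under protocol 13.1.5, is part of the primary endpoint. The mortality tests are reached only if every earlier step in the SAP 13.5.2 hierarchy succeeds. An unblinded DMC also reviews AEs by arm at least monthly.

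Finally, the examples do not all fail on one reading of 5%: 20 vs 4 is plotted with an ordinary odds ratio on the either-arm reading. This also stands, and it is a reason to state the reading.

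**Conclusion.** The point holds as a gap in reporting, not as a loss of data. Within SAP 13.6 the named safety endpoint has no treatment contrast and no interval. The single AE contrast is an odds ratio for events at 5% or more, with no zero-cell method and an undefined denominator for the cut. Efficacy is given a difference in proportions with a 95% CI, so the remedy extends to safety a measure the SAP already uses.

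The size depends on assumed counts and 250 dosed per arm. At 13 vs 0, an excess that can be stated as 5.2 points (3.1 to 8.7) becomes an odds ratio with no finite value. On the pooled reading, one-sided imbalances up to 24 vs 0 (9.6% vs 0%) are absent from the plot. The change is worth making because it is cheap and serves a stated objective. It does not threaten the primary result.

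**What to change.** - **SAP 13.6:** report the safety endpoint as a risk difference (INOpulse minus placebo) with a Miettinen-Nurminen 95% CI in the Full Safety Set. Give the same for any TEAE, any SAE and death.
- **SAP 13.6.2 and Figure 14.2.1.1:** show the risk difference with a score CI, in place of or beside the odds ratio, for AEs reaching 5% in either arm. If the odds ratio stays, name the interval method and the zero-cell rule.
- **AEs of special interest:** add a table with the same risk difference whatever the frequency. An either-arm 5% rule alone would still leave a 12 vs 2 imbalance off the plot.
- **Wording:** SAP 13.6 speaks of study discontinuation where protocol 7.3 and SAP 9.0 speak of study drug discontinuation. Reconcile these in the same edit.

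The cost is SAP text and a few lines of SAS, with no new data. The downside is more descriptive intervals without multiplicity adjustment, which the SAP should label as such.
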